6.3. Sensitivity Analysis of Primary Endpoint

The following sensitivity analyses of the primary endpoint (Change in CLASI-A total score at Week 12) will be performed:

- primary analysis repeated on hypothetical estimand
- non-parametric ANCOVA analysis using rank transformed data

6.4. Secondary Efficacy Endpoints

6.4.1. Definition of Secondary Efficacy Endpoints

Secondary efficacy endpoints include:

- Proportion of subjects at Week 12 with a decrease of ≥ 5 points in CLASI activity score from baseline
- Proportion of subjects at Week 12 with no worsening in CLASI activity score from baseline (worsening defined as ≥ 3 point increase)
- Proportion of subjects at Week 24 with a decrease of ≥ 5 points in CLASI activity score from baseline
- Proportion of subjects at Week 24 with no worsening in CLASI activity score from baseline (worsening defined as ≥ 3 point increase)

6.4.2. Analysis Methods for Secondary Efficacy Endpoint

The proportion of subjects with a decrease of ≥ 5 points in CLASI activity score and the proportion of subjects with no worsening from baseline to Week 12 will be analyzed separately using Cochran-Mantel-Haenszel (CMH) test stratified by the randomization stratification factors. If stratification leads to small cell sizes, the strata will be pooled and the Fisher's Exact test will be used.

The proportion of subjects with a decrease of ≥ 5 points in CLASI activity score from baseline to Week 24 and no worsening in CLASI-A from baseline to Week 24 will be analyzed by one-sample exact binomial test for each active treatment group.

The number and percentage of subjects with a decrease of ≥ 5 points in CLASI activity score from baseline and no worsening at Week 12 and at Week 24 will be provided. 95% CIs for the percentage will be calculated using the Clopper-Pearson exact method.

The secondary endpoints analysis will be based on the FAS. The missing response data will be imputed as No Response. The sensitivity analysis without imputation of the missing values (observed cases) will also be performed.

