8.5.2. Secondary and Exploratory Analyses

For categorical endpoints, Cochran-Mantel-Haenszel approach adjusting for the randomization stratification factors will be used. For continuous endpoints, a similar MMRM approach will be used to evaluate treatment effect on change from baseline (Day 1).

The summary statistics will be provided by treatment arm. Differences across treatment arms will be summarized and treatment comparisons may be performed. Details on efficacy analyses will be described in the statistical analysis plan (SAP).

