1. INTRODUCTION

This statistical analysis plan (SAP) describes the statistical analysis methods and data presentations to be used in tables, figures, and listings (TFLs) in the clinical study report (CSR) for Study GS-US-436-4092. This SAP is based on the study protocol amendment 4 dated 15 October 2018 and the electronic case report form (eCRF). The SAP will be finalized before the database freeze for the primary analysis. Any changes made after the finalization of the SAP will be documented in the CSR.

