1.2. Study Design

This is a Phase 2, randomized, double-blind, placebo-controlled study to evaluate the safety and efficacy of filgotinib and lanraplenib in female subjects with moderately-to-severely active CLE.

A schematic of this study is as below:

Eligible subjects will be randomized 2:2:1 in a blinded fashion to 1 of 3 arms and receive daily oral doses of the following study drugs starting on Day 1 for 12 weeks:

Table 1. **Study Treatments**

Arm	Study Drugs
Filgotinib 200 mg (n=20)	filgotinib 200 mg + PTM lanraplenib 30 mg
Lanraplenib 30 mg (n=20)	lanraplenib 30 mg + PTM filgotinib 200 mg
Placebo (n=10)	PTM filgotinib 200 mg + PTM lanraplenib 30 mg

PTM = placebo to match

On Day 1, randomization will be stratified by two factors: (i) disease subtype (chronic cutaneous lupus erythematosus [CCLE] (eg, discoid lupus erythematosus [DLE]) vs. subacute cutaneous lupus erythematosus [SCLE]) and (ii) concurrent background disease-modifying antirheumatic drug [DMARD] use vs. no use.

At Week 12, upon completion of all scheduled assessments, subjects in placebo group will be re-randomized to receive filgotinib 200 mg + PTM lanraplenib 30 mg once daily or lanraplenib 30 mg + PTM filgotinib 200 mg once daily for the remainder of the study in a blinded fashion. Dosing and assessments for all subjects will continue through Week 24.

Subjects who have not permanently discontinued study drug dosing during the first 24-week period may enter the subsequent 24-week extension period where they will continue to receive their assigned dose of study drug, in a blinded fashion.

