3. GENERAL CONSIDERATIONS FOR DATA ANALYSES

Analysis results will be presented using descriptive statistics. For categorical variables, the number and percentage of subjects in each category will be presented; for continuous variables, the number of subjects (n), mean, standard deviation (SD) or standard error (SE), median, first quartile (Q1), third quartile (Q3), minimum, and maximum will be presented.

All statistical tests will be 2-sided and performed at the 0.1 significance level unless otherwise specified.

By-subject listings will be presented for all subjects in the All Randomized Analysis Set and sorted by subject ID number, visit date, and time (if applicable). Data collected on log forms, such as adverse events, will be presented in chronological order within the subject. The treatment group to which subjects were randomized will be used in the listings. Age, sex at birth, race, and ethnicity will be included in the listings, as space permits.

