3.3. Strata and Covariates

Subjects will be randomly assigned to treatment groups via the interactive voice or web response system (IXRS) in a 2:2:1 ratio to lanraplenib 30 mg, filgotinib 200 mg and placebo using a stratified randomization schedule. Stratification will be based on the following variables:

- Disease subtype (chronic cutaneous lupus erythematosus [CCLE] vs subacute cutaneous lupus erythematosus [SCLE])
- Concurrent background systemic disease-modifying antirheumatic drug [DMARD] use

For the stratification, systemic DMARDs administration will be considered. If there are discrepancies in stratification factor values between the IXRS and the clinical database, the values recorded in the clinical database will be used in the analyses. If it is impossible to derive the stratification factor from the clinical database due to missing values then the data from IXRS will be used.

Efficacy endpoints will be evaluated using stratification factors as covariates or stratification variables for analyses, as specified in Section 6.

For efficacy endpoints, the baseline value of the efficacy variable(s) will be included as a covariate in the efficacy analysis model.

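### SAP 6.4.2 leaves its small-cell trigger undefined, and the pooled Fisher fallback has a true size of only about 3-6% at the declared 10% for response rates of 10-90%

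*SAP*

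**What the plan says.** Protocol 8.5.2 states: "For categorical endpoints, Cochran-Mantel-Haenszel approach adjusting for the randomization stratification factors will be used". It leaves further detail to the SAP.

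SAP 6.4.2 keeps CMH, stratified by the randomisation factors, for the two Week 12 endpoints (a CLASI activity decrease of at least 5 points, and no worsening). It then gives the exception: "If stratification leads to small cell sizes, the strata will be pooled", after which Fisher's exact test is used. Neither document says what counts as small, or whether it refers to subjects per stratum, observed response cells or expected counts.

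Four other statements bear on the point:
- SAP 1.2: "On Day 1, randomization will be stratified by two factors", each with two levels, so there are four strata. Planned arm sizes are 20, 20 and 10.
- SAP 3: "All statistical tests will be 2-sided and performed at the 0.1 significance level unless otherwise specified". SAP 3.5 adds no multiplicity adjustment.
- SAP 6.4.2: "The missing response data will be imputed as No Response". This keeps treated subjects in the table, so each comparison stays near 20 v 10.
- SAP 3.3: where the randomisation system and the database disagree on a stratum, "the values recorded in the clinical database will be used in the analyses". The analysed strata need not be balanced by the randomisation.

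**The concern.** The fallback is worded as an exception. With 10 placebo subjects in four strata, it may in practice be the main test, depending on a rule that is not written down. If *small* refers to response cells by arm, it can be settled only once outcomes by arm are known.

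The replacement test also does not use the level that the SAP declares. Fisher's test on a 20 v 10 table has few attainable p-values, so a nominal 10% test rejects a true null far less often than 10%. The cost is power, in a comparison with little to spare.

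**Working it through.** **The plan's own figure.** The only power figure is 79% for the primary endpoint. With 10% drop-out (18 v 9), difference 2, SD 2 and two-sided 0.1: Φ(2 / (2·√(1/18 + 1/9)) − 1.645) = Φ(2.449 − 1.645) = 78.9%. It reproduces, but says nothing about the responder endpoints, for which no rates or power are given.

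**How often the fallback fires.** The answer depends on the meaning of *small*.
- Observed cell below 2: placebo has 4 strata × 2 outcomes = 8 cells. If each held at least 2, 16 subjects would be needed; there are 10. The rule always fires.
- Expected cell below 5: in a stratum with 9 or fewer placebo subjects, the two expected placebo counts sum to at most 9, so one is below 5. The rule fires for any split over two or more strata.
- Any zero cell: 92-100% of simulated trials.
- Mantel-Fleiss criterion (at least 5): not met in at least 93% of simulated trials.
- A stratum with at most one placebo subject: about 25% of simulated trials with balanced strata, and 78-100% with unbalanced strata (assumed SCLE share 20-30%, DMARD use 50-80%).

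**True size of pooled Fisher.** For a common response rate p, sum over all 21 × 11 outcomes (a, b):

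size(p) = Σ Bin(a; 20, p) · Bin(b; 10, p) · 1[Fisher p-value ≤ 0.10]

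| Common rate | True size at nominal 10% |
|---|---|
| 5% or 95% | 0.9% |
| 10% or 90% | 3.2% |
| 20% or 80% | 5.7% |
| 30% or 70% | 5.4% |
| 50% | 5.2% |
| Maximum over all rates | 5.75% |

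At 18 v 9, as might arise in the observed-case sensitivity analysis, the maximum is 6.2%.

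**An exact test that uses the level better.** Boschloo's unconditional test, with tables ordered by the two-sided Fisher p-value, rejects at 20 v 10 when that p-value is at most 0.1216. Its maximum size over all common rates is 9.5%. Its rejection region contains Fisher's (0.1216 > 0.10), so it cannot have less power.

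**Power at 20 v 10** (placebo v active rates are assumed). Fisher, Boschloo and unstratified CMH are exact. Stratified CMH is simulated with strata 7, 5, 5, 3 v 4, 2, 2, 2 and no stratum effects.

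| Rates | Fisher | Boschloo | CMH, stratified | CMH, no strata |
|---|---|---|---|---|
| 20 v 60% | 57.7% | 68.5% | 69.7% | 69.4% |
| 40 v 90% | 85.6% | 88.4% | 90.9% | 91.6% |
| 70 v 95% | 49.2% | 57.7% | 61.5% | 61.5% |

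The last two columns nearly agree, so the gap to Fisher is due to discreteness and not to stratification. Over 13 rate pairs (10 v 40% to 80 v 95%), stratified CMH minus Fisher is 5-13 points with balanced strata and no stratum effects, 7-19 with strong stratum effects, and 2-13 when the stratum mix is random. Boschloo minus Fisher is 3-12 points over the same pairs. CMH is significant and Fisher not in 4-19% of simulated trials.

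**Worked example: 11/20 v 2/10.** Fisher gives p = 0.119. Take strata of 6, 6, 4, 4 v 3, 3, 2, 2 with responders 3, 3, 3, 2 v 1, 1, 0, 0. The expected active responders are 2.667 + 2.667 + 2 + 1.333 = 8.667, and the variance is 0.556 + 0.556 + 0.400 + 0.356 = 1.867. CMH is (11 − 8.667)² / 1.867 = 2.917, p = 0.088. Mantel-Fleiss is 4.33, below 5. Boschloo gives p = 0.087. The same data fall on either side of 0.1 according to the test.

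**The case against.** The strongest reply is that the SAP never states the rules that make the fallback near certain. The expected-count rule also proves too much. In the unstratified 20 v 10 table with m responders, the expected placebo cells are m/3 and 10 − m/3, and both reach 5 only at m = 15. That rule fires almost regardless of strata, which fits poorly with wording about stratification *leading to* small cells. This stands: a reader might infer that CMH will always be replaced, but the documents support that only under a conventional cell-count reading.

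Moving to an exact test when a large-sample approximation is doubtful is ordinary practice, and Fisher protects the level. Keeping asymptotic CMH where Mantel-Fleiss fails exchanges a guaranteed level for power. With strata 10, 6, 3, 1 v 5, 3, 1, 1 and a 50% rate, CMH size was 10.7% and 10.9% in two simulations. This stands too, so CMH-only is an option and not a necessary correction.

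A reader might also infer that the power is lost because Fisher ignores the strata. The unstratified CMH figures show otherwise, and the documents do not say how prognostic the two factors are.

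Finally, little depends on these p-values. No power is claimed for them, the SAP calls the study proof-of-concept, and proportions with Clopper-Pearson intervals are reported in any case. That limits the weight, but it does not justify an undefined trigger or an exact test that another exact test dominates.

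**Conclusion.** The point holds as a minor one, with two parts. First, the choice of Week 12 responder test is not fixed, because its trigger is undefined. Conventional readings trigger the fallback in nearly every trial, while a looser one does so in anything from about 25% to 100%. Second, the fallback is needlessly conservative: 3.2-5.75% true size at a declared 10% for rates of 10-90%, and 0.9% at 5% or 95%. The extreme rates could matter for the no-worsening endpoint if nearly all subjects meet it.

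The size figures assume 20 v 10 pairwise comparisons of each active arm with placebo. The power and trigger frequencies also rest on assumed response rates, stratum shares and stratum effects.

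The documents do not support three stronger readings. Type I error is not inflated by the plan as written, because Fisher errs on the safe side. The SAP does not contradict the protocol, which delegates the details. Nothing shows that the test would be chosen to suit the result; the text merely fails to rule it out. The primary MMRM, the Week 24 one-sample tests and the Clopper-Pearson intervals are unaffected.

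**What to change.** Amend the fallback sentence in SAP 6.4.2 while this is still open: "The SAP will be finalized before the database freeze for the primary analysis". Remove the undefined trigger and settle the test in one of two ways.

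(a) Keep stratified CMH with a pooled fallback, but put Boschloo's unconditional exact test in Fisher's place. State that tables are ordered by the two-sided Fisher p-value, since software differs on the two-sided version. Give a numeric trigger that uses only subjects per stratum and arm, never outcomes; a stratum with at most one placebo subject would be one such rule. The pooled test then holds the 0.1 level (maximum 9.5% at 20 v 10) and never has less power than Fisher. Like Fisher, it ignores the strata.

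(b) Optionally, make stratified CMH without continuity correction the test in all cases, with p set to 1 if its variance is zero and a pooled exact test as a sensitivity analysis. This stays closest to the protocol. The price is an approximate level, which can reach about 10.7-11% in some stratum layouts, and a gain over Fisher that falls to 2 points in the least favourable setting examined.

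Either change takes a sentence or two of SAP text and little programming. No data collection or sample size changes.

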6.5. Exploratory Efficacy Endpoints

6.5.1. Definition of Exploratory Efficacy Endpoints

Exploratory efficacy endpoints include:

[figure not shown]
Term	Percentage
GMOs	~75%
Organic	~70%
Natural	~70%
Artificial	~95%
Organic	~75%
Natural	~75%
Artificial	~95%
Organic	~75%
Natural	~75%
Artificial	~95%
Organic	~75%
Natural	~75%
Artificial	~95%

cc1

6.5.2. Analysis Methods for Exploratory Efficacy Endpoints

CCI [REDACTED]
[REDACTED]

CCI

6.6. Changes From Protocol-Specified Efficacy Analyses

The treatment policy and hypothetical estimands have been added to the analyses of the primary endpoint.

7. SAFETY ANALYSES

The safety analyses will be performed for the placebo-controlled treatment period up to Week 12, up to Week 24, and for the entire study duration. Analyses for these treatment periods will be presented by the treatment groups specified in Section 3.

For the analyses of adverse events that include data after Week 12 the exposure-adjusted analyses will be presented.

For the AEs, laboratory abnormalities and concomitant medication data, the collection/start date will be used to determine which reporting period the record belongs to. For other parameters, the nominal visits will be used.

7.1. Adverse Events and Deaths

7.1.1. Adverse Event Dictionary

Clinical and laboratory adverse events (AEs) will be coded using the current version of MedDRA. System organ class (SOC), high-level group term (HLGT), high-level term (HLT), preferred term (PT), and lower-level term (LLT) will be provided in the AE dataset.

7.1.2. Adverse Event Severity

Adverse events are graded by the investigator as Grade 1, 2, 3, 4, or 5 according to toxicity criteria specified in the protocol (CTCAE 4.03). The severity grade of events for which the investigator did not record severity will be categorized as “missing” for tabular summaries and data listings. The missing category will be listed last in summary presentation.

7.1.3. Relationship of Adverse Events to Study Drug

Related AEs are those for which the investigator selected “Related” on the AE CRF to the question of “Related to filgotinib/placebo” or “Related to lanraplenib/placebo”. If AE is reported as “Related” to any of 2 study drugs then the AE is considered “Related to study treatment”. Relatedness will always default to the investigator’s choice, not that of the medical monitor. Events for which the investigator did not record relationship to study drug will be considered related to study drug for summary purposes. However, by-subject data listings will show the relationship as missing.

7.1.4. Serious Adverse Events

Serious adverse events (SAEs) will be identified and captured as SAEs if the AEs met the definitions of SAEs that were specified in the study protocol. SAEs captured and stored in the clinical database will be reconciled with the SAE database from the Pharmacovigilance & Epidemiology Department before data finalization.

7.1.5. Treatment-Emergent Adverse Events

7.1.5.1. Definition of Treatment-Emergent Adverse Events

Treatment-emergent adverse events (TEAEs) of the entire study duration are defined as 1 or both of the following:

- Any AEs with an onset date on or after any study drug start date and no later than 30 days after permanent discontinuation of any study drug
- Any AEs leading to premature discontinuation of study drug.

TEAEs up to Week12/24 are defined as 1 or both of the following:

- Any AEs with an onset date on or after Day 1, prior to start of Week 12/24 treatment and no later than the day before the Week 12/24 treatment start date. For subjects who discontinued treatment prior to Week 12/24 visit, any AEs with an onset date on or after the study drug start date and no later than 30 days after permanent discontinuation of study drug
- Any AEs leading to premature discontinuation of study drug prior to first Week 12/24 dosing

7.1.5.2. Incomplete Dates

If the onset date of the AE is incomplete and the AE stop date is not prior to the first dosing date of study drug, then the month and year (or year alone if month is not recorded) of onset determine whether an AE is treatment emergent. The event is considered treatment emergent if both of the following 2 criteria are met:

- The AE onset is the same as or after the month and year (or year) of the first dosing date of study drug, and
- The AE onset date is the same as or before the month and year (or year) of the date corresponding to 30 days after the date of the last dose of study drug

An AE with completely missing onset and stop dates, or with the onset date missing and a stop date later than the first dosing date of study drug, will be considered to be treatment emergent. In addition, an AE with the onset date missing and incomplete stop date with the same or later month and year (or year alone if month is not recorded) as the first dosing date of study drug will be considered treatment emergent.

7.1.6. Summaries of Adverse Events and Deaths

Treatment-emergent AEs will be summarized based on the Safety Analysis Set. The tables will be presented by treatment period: placebo-controlled period (up to Week 12) and for weeks 12-48. The overall summary of TEAEs may also be provided for the entire study duration.

The number and percentage of subjects who experienced at least 1 TEAE will be provided and summarized by SOC, HLT, PT, and treatment group. For other AEs described below, summaries will be provided by SOC, PT, and treatment group:

- All TEAEs
- TEAEs of Grade 3 or higher (by maximum severity)
- All TE treatment-related AEs
- TE treatment-related AEs of Grade 3 or higher (by maximum severity)
- All TE SAEs
- All TE treatment-related SAEs
- All TEAEs leading to premature discontinuation of study drug
- All TEAEs leading to premature discontinuation of study
- All TEAEs leading to death (i.e. outcome of death)

A brief, high-level summary of AEs described above will be provided by treatment group and by the number and percentage of subjects who experienced the above AEs. All deaths observed in the study will also be included in this summary.

Multiple events will be counted only once per subject in each summary. Adverse events will be summarized and listed first in alphabetic order of SOC and HLT within each SOC (if applicable), and then by PT in descending order of total frequency within each SOC. For summaries by severity grade, the most severe grade will be used for those AEs that occurred more than once in an individual subject during the study.

In addition to the above summary tables, all TEAEs and TE treatment-related AEs will be summarized by PT only, in descending order of total frequency.

The data listings will be provided for the following:

- All AEs, indicating whether the event is treatment emergent
- All AEs of Grade 3 or higher
- SAEs
- Deaths
- AEs leading to premature discontinuation of study drug
- AEs leading to premature discontinuation of study

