7. ADVERSE EVENTS AND TOXICITY MANAGEMENT

7.1. Definitions of Adverse Events, Adverse Reactions, and Serious Adverse Events

7.1.1. Adverse Events

An adverse event (AE) is any untoward medical occurrence in a clinical study subject administered a medicinal product, which does not necessarily have a causal relationship with the treatment. An AE can therefore be any unfavorable and/or unintended sign, symptom, or disease temporally associated with the use of a medicinal product, whether or not considered related to the medicinal product. AEs may also include pre- or post-treatment complications that occur as a result of protocol specified procedures, lack of efficacy, overdose, drug abuse/misuse reports, or occupational exposure. Preexisting events that increase in severity or change in nature during or as a consequence of participation in the clinical study will also be considered AEs.

An AE does not include the following:

- Medical or surgical procedures such as surgery, endoscopy, tooth extraction, and transfusion. The condition that led to the procedure may be an adverse event and must be reported.
- Pre-existing diseases, conditions, or laboratory abnormalities present or detected before the screening visit that do not worsen
- Situations where an untoward medical occurrence has not occurred (eg, hospitalization for elective surgery, social and/or convenience admissions)
- Overdose without clinical sequelae (see Section 7.7.1)
- Any medical condition or clinically significant laboratory abnormality with an onset date before the consent form is signed and not related to a protocol-associated procedure is not an AE. It is considered to be pre-existing and should be documented on the medical history eCRF.

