7.2.2. Assessment of Severity

The severity of AEs will be graded using the modified Common Terminology Criteria for Adverse Events (CTCAE), version 4.03. For each episode, the highest grade attained should be reported.

If a CTCAE criterion does not exist, the investigator should use the grade or adjectives: Grade 1 (mild), Grade 2 (moderate), Grade 3 (severe), Grade 4 (life-threatening) or Grade 5 (fatal) to describe the maximum intensity of the adverse event. For purposes of consistency with the CTCAE, these intensity grades are defined in Table 3 and Appendix 4.

Table 3. Grading of Adverse Event Severity

Grade	Adjective	Description
Grade 1	Mild	Asymptomatic or mild symptoms; clinical or diagnostic observations only; intervention not indicated
Grade 2	Moderate	Local or noninvasive intervention indicated; limiting age-appropriate instrumental ADL
Grade 3	Severe	Severe or medically significant but not immediately life-threatening; hospitalization or prolongation of hospitalization indicated; disabling; limiting self-care ADL
Grade 4	Life-threatening	Urgent intervention indicated
Grade 5	Death	Death related AE

^{*} Activities of Daily Living (ADL) Instrumental ADL refer to opening preparing meals, shopping for groceries or clothes, using the telephone, managing money, etc.

7.3. Investigator Requirements and Instructions for Reporting Adverse Events and Serious Adverse Events to Gilead

Requirements for collection prior to study drug initiation:

After informed consent, but prior to initiation of study medication, the following types of events should be reported on the eCRF: all SAEs and adverse events related to protocol-mandated procedures.

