A baseline laboratory value for the placebo-controlled and entire study period will be defined as the last nonmissing measurement obtained on or prior to the date/time of first dose of any study drug. For the active treatment period, the baseline for the subjects originally randomized to placebo will be the measurement before or on the day when the first dose of active study treatment is administered.

A by-subject listing for laboratory test results will be provided by subject ID number and visit in chronological order for hematology, serum chemistry, and urinalysis separately. Values falling outside of the relevant reference range and/or having a severity grade of 1 or higher on the Common Terminology Criteria for Adverse Events (CTCAE severity grade) will be flagged in the data listings, as appropriate.

No formal statistical testing is planned.

7.2.1. **Summaries of Numeric Laboratory Results**

Descriptive statistics will be provided by treatment group for the following laboratory tests:

- Hematology
 - Hematocrit
 - Hemoglobin
 - Platelet count
 - Red blood cell count
 - White blood cell (WBC) count
 - Mean corpuscular volume

- Lymphocytes
- Monocytes
- Neutrophils
- Eosinophils
- Basophils
- Chemistry
 - Alanine aminotransferase (ALT)
 - Aspartate aminotransferase (AST)
 - Alkaline phosphatase (ALP)
 - Total bilirubin
 - Serum creatinine
 - Creatinine clearance by Cockcroft-Gault formula
 - Creatine phosphokinase (CPK)
 - Glucose
- Lipid Panel
 - Triglycerides
 - Total cholesterol
 - HDL
 - LDL
 - LDL/HDL ratio

Fasting results for lipid profile and serum glucose will be presented separately from overall results.

Change from baseline to a postbaseline visit will be defined as the visit value minus the baseline value. The mean, median, Q1, Q3, minimum, and maximum values will be displayed to the reported number of digits; SD values will be displayed to the reported number of digits plus 1.

Median (Q1, Q3) of the observed values for the laboratory tests specified above will be plotted using a line plot by treatment group and visit.

In the case of multiple values within the visit, data will be selected for analysis as described in Section 3.8.3.

7.2.2. **Graded Laboratory Values**

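### A continuous adverse event that starts on placebo and worsens after the Week 12 switch is tabulated at its post-switch grade in the placebo column and is absent from the Weeks 12-48 table

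*SAP*

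**What the plan says.** - **Collection.** Protocol 7.2.2: "For each episode, the highest grade attained should be reported".
- **Allocation to a period.** SAP 7 says that for AEs "the collection/start date will be used to determine which reporting period the record belongs to". SAP 7.1.5.1 defines treatment-emergent AEs up to Week 12 or 24 by onset: "Any AEs with an onset date on or after Day 1, prior to start of Week 12/24 treatment". Neither section has a rule for an event that worsens later, and 7.1.5.1 gives no separate definition for Weeks 12-48.
- **Presentation.** SAP 7.1.6 splits the AE tables by period: "placebo-controlled period (up to Week 12) and for weeks 12-48". They include AEs of Grade 3 or higher by maximum severity, and serious AEs. For repeated AEs, "the most severe grade will be used for those AEs that occurred more than once in an individual subject during the study". A whole-study table is optional: "The overall summary of TEAEs may also be provided for the entire study duration".
- **Switch.** Under protocol 3.3, placebo subjects are re-randomized 1:1 to filgotinib or GS-9876 (called lanraplenib in the SAP) after the Week 12 assessments.
- **Laboratory data.** For the active treatment period, SAP 7.2 resets the reference point: "the baseline for the subjects originally randomized to placebo will be the measurement before or on the day" of the first active dose. SAP 7.2.2.1 uses the same reset for treatment-emergent abnormalities. AEs have no counterpart.

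**The concern.** The first 12 weeks are the only placebo-controlled safety comparison in the trial. If an AE keeps its start date but takes its worst grade from any later time, then for a placebo subject that grade may have been reached on a different treatment. The placebo column up to Week 12 then shows severity or seriousness that arose on filgotinib or lanraplenib, and the Weeks 12-48 table does not show it. Infection is a plausible route: protocol 1.5 calls serious infection an important potential risk for filgotinib, and SAP 7.1.7 makes serious infections an AE of special interest. An infection that starts late in the placebo period and becomes serious after the switch would follow exactly this path. The laboratory sections show that the SAP recognises the problem for graded laboratory values.

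**Working it through.** The documents give no AE rates, so there is no planned figure on this point to reproduce. The sample-size statement supplies only the arm sizes and the drop-out assumption; its 79% power is unaffected.

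**Inputs.** Arms of 20, 20 and 10 (protocol 8.9). A 10% drop-out per arm (same section), which leaves 9 of 10 placebo subjects if all of it falls before the switch. Re-randomization 1:1, so about 5 switched subjects per drug.

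**Step 1: trace one record (assumed example).** An AE starts at Week 10 on placebo at Grade 1 and reaches Grade 3 at Week 16 on active drug, without a gap. Protocol 7.2.2 gives one episode with Grade 3. SAP 7 and 7.1.5.1 give a Week 10 start, hence the period up to Week 12. SAP 7.1.6 then tabulates it by maximum severity.

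| Grade 3+ table | As written | Grade limited to period, worsening recorded as a new AE |
|---|---|---|
| Placebo column, up to Week 12 | 1/10 = 10% | 0/10 = 0% (AE stays there at Grade 1) |
| Weeks 12-48, switched column of about 5 | 0/5 = 0% | 1/5 = 20% |
| Weeks 12-48, switched subjects pooled with the 20 on that drug from Day 1 | 0 from this event | 1/25 = 4% from this event |

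The same trace applies to an AE that becomes serious after the switch.

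**Step 2: effect on the between-arm difference.** The rule applies in every arm. Let e_P be the number of placebo subjects, and e_A the number in one active arm, whose AE started before Week 12 but reached Grade 3+ only afterwards. Suppose none of them is already counted at Grade 3+. The rule shifts the difference (active minus placebo), in percentage points, by

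100 × (e_A/20 − e_P/10).

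- e_P = 1, e_A = 0: 0 − 10 = −10
- e_P = 1, e_A = 1: 5 − 10 = −5
- e_P = 1, e_A = 2: 10 − 10 = 0

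The full 10 points reach the difference only if no active-arm AE does the same. If such worsening is equally frequent per subject in both arms, the expected shift is zero. The documents give neither count. What is particular to placebo is the attribution: in an active arm the later grade was reached on the same drug, in the placebo column on another one.

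**Step 3: how likely is at least one such event?** With an assumed risk q per switched subject, the chance is 1 − (1 − q)^n, for n = 9 to 10:

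- q = 2%: 17-18%
- q = 5%: 37-40%
- q = 10%: 61-65%
- q = 20%: 87-89%

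These q values are assumptions, not figures from the documents.

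**Step 4: timing.** The Week 12 analysis runs once every subject has reached Week 12 or left (SAP 2.2). By then only earlier-enrolled switchers have much time on active drug. Post-switch follow-up of up to 48 − 12 = 36 weeks is reached only at the final analysis, by those who complete the extension.

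**The case against.** The strongest case against is that allocation by onset is a stated, common rule applied to every arm, in a small proof-of-concept study with no formal AE test described. The events are not lost. SAP 7.1.6 lists all AEs of Grade 3 or higher and all serious AEs, and a whole-study summary would show these subjects in the placebo-to-active groups of SAP 3.2. With about 10 placebo subjects, each case can be checked by hand against the switch date. All of that stands and limits the consequence. It does not correct the period tables, and SAP 7.1.6 makes the whole-study AE summary optional.

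Four stronger readings are tempting but not supported:

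- *A recurrence on active drug raises the grade of an earlier placebo event.* A reader might infer this from the study-wide window in SAP 7.1.6. But a recurrence has its own start date, so SAP 7 places it after Week 12 and 7.1.5.1 keeps it out of the earlier table. The sentence reads as a tie-break among events already in a table. It also covers only AEs that occur more than once, so the continuous case rests mainly on protocol 7.2.2 with SAP 7 and 7.1.5.1.
- *AEs are ascertained differently by arm.* Protocol 7.1.1 counts as AEs "Preexisting events that increase in severity or change in nature" during study participation. That concerns conditions present beforehand and applies to all arms alike.
- *The grade at the switch is irrecoverable.* AE recording is delegated to eCRF completion guidelines that are not among the documents. They may already require a new record on worsening, and AEs are reviewed at every visit.
- *The comparison is biased by 10 points per event.* Step 2 shows why this does not follow.

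**Conclusion.** The gap is real but narrow. Followed as written, the rules charge on-drug worsening of a continuous placebo-onset AE to the placebo column and leave it out of the Weeks 12-48 table, whereas graded laboratory abnormalities are re-baselined at the first active dose. At most about 10 subjects are exposed. Each such event moves the placebo Grade 3+ or serious rate by about 10 points; the net bias in the between-arm difference is smaller than that and cannot be quantified from the documents.

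This rests on three assumptions: that a worsening AE stays one episode on the eCRF; that Weeks 12-48 membership follows the start-date rule, since no separate definition is given; and that at least one such event occurs. The plan does not hide these events, since they remain in the listings. The change is worth making because it is cheap and protects the only placebo-controlled safety table.

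**What to change.** 1. SAP 7.1.6: make the window for the most severe grade the reporting period rather than the study.
2. eCRF completion guideline: if an AE ongoing at the first Week 12 dose later increases in grade or becomes serious, record the worsening as a new AE with the date of worsening as its onset. Apply this to all subjects, so that the blind is kept. If the guideline already requires it, confirm this in the SAP.
3. SAP 7.1.5.1: count such worsening as treatment-emergent in the Weeks 12-48 tables, which also supplies part of the missing definition for that period.

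The cost is one sentence in the guideline and two in the SAP. Treatment, visits, endpoints and power do not change. The downside is that some episodes appear as two records, so event counts rise slightly; subject counts within a period are not inflated, because SAP 7.1.6 counts each subject once per summary.
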